## **Data and Statistical Methods**

**Aim 1**: to compare the incidence of urinary retention following retropubic midurethral sling placement in those women receiving normal saline vs lidocaine for retropubic hydrodissection. Rates of postoperative urinary retention will be compared between groups using chi squared testing. Duration of urinary retention measured in days will be compared using t-tests or nonparametric testing as appropriate. To adjust for other factors that may impact voiding trial results, logistic regression analysis will be performed and will include variables identified as significant (p>0.01) on univariable analysis as well as intraoperative narcotic use, age, and estimated blood loss. All analyses will be performed using intention to treat. Data analyses will be done using SPSS and Matlab.

**Aim 2**: to assess postoperative pain in women receiving retropubic normal saline vs lidocaine during midurethral sling placement. VAS scores will be measured on a scale of 0-100mm with higher scores indicating worse pain. Change from baseline in VAS pain scores will be compared at each time point with t-tests. Narcotic requirements measured in morphine equivalent grams will be compared by t-tests (and

Wilcoxon rank-sum tests if non-parametric). Both VAS pain scores and narcotic requirements will be compared in an intention to treat analysis. Multivariable logistic regression analyses will be used to identify independent risk factors that predict pain at 2, 6 and 24 hours postoperatively. We plan to adjust for operating time, estimated blood loss, urinary retention, and concomitant procedures, as all of these may predict worse postoperative pain. Anything found to be different at baseline will also be included as covariates.

**Aim 3**: to assess patient satisfaction in women receiving retropubic normal saline vs lidocaine during midurethral sling placement. Patient satisfaction Likert scale questionnaires will be compared using t-tests with lower scores indicating worse satisfaction. T-tests (and Wilcoxon rank-sum tests if non-parametric) will be used to analyze results of individual APS-POQ-R questions.

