Inclusion criteria includes the following: age 18 years or older, English speaking, and competent to give consent. Exclusion criteria includes a known intolerance or allergic reaction to local anesthetics, planned spinal anesthesia for the procedure, planned concomitant prolapse repair other than anterior repair, or preoperative voiding dysfunction as evidenced by a post-void residual (PVR) of 150 mL or greater. On average, our institution treats 60-80 patients per year with midurethral slings.

Informed consent will be obtained at the preoperative appointment. Demographic information including age, weight, height, body mass index (BMI), allergies, obstetrical, gynecological, medical, and surgical history will be collected from those subjects who agree to participate. Preoperative bladder testing obtained as part of routine clinical care will also be recorded,

Patients will be randomized in the preoperative area on the day of surgery to prevent randomization of patients who may go on to cancel or postpone surgery. Randomization will be created using a random numbers table with blocking into groups of 4. On the day of surgery, the operating room pharmacist will prepare 20 cc of either study drug, 0.5% lidocaine with epinephrine 1:200,000, or normal saline with epinephrine 1:200,000 in identical appearing 20cc syringes to be injected retropubically. Our group's routine clinical practice will inject the randomly assigned 20cc syringe retropubically along the path of the midurethral sling trocars. Suburethral injection of local anesthetic will be performed at surgeon discretion. Surgical teams, anesthesia teams and patients will be blinded to allocation assignment. The investigational drug pharmacist will maintain the randomization sequence.

Standard postoperative care will then be followed. Before discharge, as part of routine clinical care, all subjects will undergo a postoperative voiding trial as outlined below. A routine postoperative evaluation will be performed by the primary surgeon at a 6-week interval following surgery.

Table 1. Timeline of data collection

	Time of Data Collection/Eval						itions	
Data	Baseline	Intervention	Surgery	Pos	stoperative as			
				2 h	6 h	24h	Week 1	Week 6
				(+-30	(+- 30			
				mins)	mins)			
Retrograde Voiding Trial				Х				
VAS pain score	Х			Х	Х			
Narcotic requirements	Х		Х	Х	Х	Х	х	
Pain Diary						Х	х	
Demographic factors	Х							
Intraoperative factors			Х					
Side effects (APS-POQ-R)						Х		

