#### Variables and measures

## Postoperative Urinary Retention

The primary outcome is postoperative voiding trial failure, defined as being discharged from the hospital with an indwelling catheter or instructions for clean intermittent self-catheterization (CISC). Duration of catheterization will also be measured and recorded on the postoperative diary. As part of routine clinical care, a retrograde voiding trial will be completed 1-2 hours postoperatively using the following protocol and parameters:

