# **Sample Size Calculation**

The rate of postoperative urinary retention following midurethral sling at our institution is 35% (data unpublished). To detect a clinically significant reduction of postoperative urinary retention of 20%, 72 subjects per group would be needed to provide 80% power with a two-sided alpha of 0.05. After adjusting for a 5% loss to follow-up rate, 75 subjects per arm would be required.

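### Preoperative post-void residual is not prespecified as a covariate for the primary outcome; adjusting for it would cost little and might add about 0 to 4 points of power

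*Combined protocol and SAP*

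**What the plan says.** The section on postoperative urinary retention states: "The primary outcome is postoperative voiding trial failure", a yes/no outcome. The Aim 1 paragraph of Data and Statistical Methods gives the test: "Rates of postoperative urinary retention will be compared between groups using chi squared testing". No baseline value enters that comparison.

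The same paragraph plans a logistic regression to adjust for other influences on the voiding trial. Its fixed terms are age, narcotics given during surgery and blood loss. Other variables enter by univariable significance, with the threshold printed as p>0.01. PVR is not named.

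Study Entry and Recruitment excludes women with "preoperative voiding dysfunction as evidenced by a post-void residual (PVR) of 150 mL or greater", so PVR has to be known before randomisation. It adds: "Preoperative bladder testing obtained as part of routine clinical care will also be recorded".

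The Sample Size Calculation starts from an institutional retention rate of 35% and a reduction of 20%. It concludes that "72 subjects per group would be needed to provide 80% power with a two-sided alpha of 0.05" and then that "After adjusting for a 5% loss to follow-up rate, 75 subjects per arm would be required".

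**The concern.** PVR describes how well the bladder empties before surgery, and the primary outcome is failure of an emptying test after surgery. Among the baseline values that the plan mentions, PVR is a natural candidate to predict the outcome, although that is a judgement and not something the documents show. When a baseline value is prognostic, adjusting the arm comparison for it usually gives more power at the same sample size. It also accounts for chance imbalance in that value.

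The design has little slack. Power sits at the 80% target, and extra patients are hard to find: 60 to 80 sling patients a year over two years is 120 to 160 women before exclusions and refusals, against a target of 2 × 75 = 150.

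The planned logistic regression does not fill the gap. PVR's inclusion would depend on a screen of the trial's own data, and two of the fixed terms, narcotic use and blood loss, arise after randomisation. Such a model is not a clean baseline-adjusted comparison of the arms.

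**Working it through.** **Inputs from the documents**
- Failure rates of 35% and 15%, reading the 20% reduction as percentage points. A relative reduction (35% to 28%) would need 691 per group, which does not match the plan.
- 72 per group, two-sided alpha 0.05, 80% power; 75 per arm after 5% loss.
- Unadjusted chi-squared test.

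**Input the documents do not give**
- The correlation rho between preoperative PVR (below 150 mL) and voiding-trial failure. Assumed range: 0 to 0.3.

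**Step 1: reproduce the plan's sample size.** With the mean rate 0.25 used under the null:

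n = [1.96 × √(2 × 0.25 × 0.75) + 0.842 × √(0.35 × 0.65 + 0.15 × 0.85)]² / 0.20² = (1.200 + 0.501)² / 0.04 ≈ 72.4

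This rounds up to 73, against the stated 72. The stated figure is reproduced to within rounding.

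**Step 2: power of the planned test at 72 per arm.**
- se0 = √(2 × 0.25 × 0.75 / 72) = 0.0722
- se1 = √((0.2275 + 0.1275) / 72) = 0.0702
- Power = Φ((0.20 − 1.96 × 0.0722) / 0.0702) = Φ(0.834) = 79.8%

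With 75 × 0.95 = 71.25 evaluable per arm, power is 79.4%.

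**Step 3: power after adjustment for PVR.** As an approximation, multiply both standard errors by √(1 − rho²):

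| Assumed rho | √(1 − rho²) | Power | Gain (points) |
|---|---|---|---|
| 0 | 1.000 | 79.8% | 0 |
| 0.1 | 0.995 | 80.2% | 0.4 |
| 0.2 | 0.980 | 81.4% | 1.6 |
| 0.3 | 0.954 | 83.4% | 3.6 |

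For example, at rho = 0.3: Φ((0.20 − 0.1349) / 0.0670) = Φ(0.971) = 83.4%.

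**Step 4: check by simulation.** There were 4,000 trials per setting with 72 per arm and marginal rates held at 35% and 15%. PVR was drawn from an assumed skewed distribution cut off at 150 mL. The chi-squared test was compared with the likelihood-ratio test for arm in a logistic model containing PVR.

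| Odds ratio per SD of PVR | Chi-squared | PVR-adjusted |
|---|---|---|
| 1 | 81.8% | 81.4% |
| 1.25 | 81.0% | 80.8% |
| 1.5 | 81.6% | 82.7% |
| 2 | 81.0% | 83.8% |

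Monte Carlo error is about 0.6 points. An odds ratio of 2 corresponds to a squared correlation of 0.103 at the 35% rate and 0.075 at the 15% rate, so rho is roughly 0.3. The simulated gain there, 2.8 points, is in line with Step 3. A second simulation with a normally distributed covariate (3,000 runs per setting) gave about 82% adjusted against 80% unadjusted at rho 0.2. With no correlation the two tests were 0.3 points apart (79.4% and 79.7%).

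**Step 5: type I error.** In the skewed-PVR simulation, rejection under the null was 5.2% to 5.8% with adjustment and 4.7% to 5.5% for chi-squared. In the normal-covariate simulation (2,000 runs per setting for this check), the adjusted test ran from 4.5% to 6.3%. These figures are close to the nominal 5%, but they do not show that there is no increase at all.

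**The case against.** The strongest reply is that nothing here is wrong. Chi-squared is a valid test of a binary outcome in a randomised trial, and it matches the sample size calculation. This stands in full.

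A second reply is that the benefit is unproven. The documents contain no estimate of PVR's prognostic strength. Excluding values of 150 mL or more removes the women with the poorest emptying, which tends to weaken prediction. The outcome is also an acute response to surgery after a 300 mL backfill, which is not the same thing as a resting residual. This stands too: a gain near zero is as compatible with the documents as one of 3 or 4 points.

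A reader might infer that the trial is certainly giving up power, perhaps 5 to 10 points. The same formula gives 84.8% at rho 0.35 and 89.9% at rho 0.5. But rho of about 0.35 needs an odds ratio above roughly 2.5 per SD of PVR, and rho near 0.5 needs one above roughly 5. No part of the documents supports values of that size.

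A third reply is that a strongly prognostic PVR would probably be picked up by the planned screen. That is only a partial answer. Selection would depend on the data, and the resulting model would still contain terms measured after randomisation.

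Finally, the change is not quite free. The documents do not state how or when PVR is measured, or that its numeric value is kept, so completeness is an inference from the eligibility rule.

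**Conclusion.** The point holds as a modest, optional improvement. The primary test is valid and has about its stated power. What is missing is prespecified adjustment for a pre-randomisation measure of bladder emptying that eligibility already requires.

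The possible gain is about 0 to 4 points of power (79.8% to 83.4%), with type I error close to nominal and essentially no loss if PVR is not prognostic. This rests on an assumed correlation of 0 to 0.3, on 35% against 15% with 72 per arm, and on a usable numeric PVR for nearly all women.

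The documents do not support reading this as a biased or underpowered primary analysis. Nor does the point question the 150 mL entry limit.

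**What to change.** In the Aim 1 paragraph of Data and Statistical Methods, before unblinding:

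- Make the primary analysis a logistic regression of voiding-trial failure on arm and preoperative PVR (continuous) only, and take the arm test from that model.
- Report the standardised risk difference with a 95% CI, naming the variance method. The model's odds ratio is conditional on PVR and does not itself give the difference in rates on which the trial was sized.
- State that the numeric preoperative PVR is recorded, and fix a simple rule for missing values, for example mean imputation.
- Keep the chi-squared test as a supporting analysis.

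The cost is mainly wording, with no new visits or patients. The downsides are a somewhat less simple primary analysis, the need for a missing-PVR rule, and a gain that may be small or nil.

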## **Study Entry and Recruitment**

Subjects with stress incontinence or stress-predominant mixed urinary incontinence who are scheduled to undergo a retropubic midurethral sling with or without concomitant anterior repair at West Penn Hospital, Bethel Park Health and Wellness Pavilion, Wexford Health and Wellness Pavilion, and Jefferson Hospital of the Allegheny Health Network, will be offered participation in the study. Study subjects may also be recruited via the MyChart app. The MyChart app is a secure app accessible only by the patient. Only the patient can access their medical information through this app by setting up a secure account using their social security number, birthday, username, and password. The patient can log in securely by providing their username and password, or via biometrics (i.e., face recognition). If the research staff reaches out to the subject via telephone and the subject does not answer, a follow-up message will be sent to the subject via the MyChart app, with the statement that initial contact attempt was made by phone. The message will include the following:

A recent review of your records indicated that you may be eligible to participate in an ongoing research study. The Retropubic Lidocaine study is looking to determine if the numbing medicine we standardly use during surgery impacts your ability to empty your bladder postoperatively. If you are interested in participating, you would be randomly selected to get our standard numbering medicine (lidocaine and epinephrine) or placebo (saline and epinephrine) at the two sling exit sites in your pubic area while in the operating room. This study does not require any additional in-person visits. There will be a few questionnaires we would ask you to complete during your recovery. If you are interested in learning more about our study, please call [contact], or email [contact]. If you respond to this message indicating your interest, you are giving your permission for the study staff to receive your phone number and/or email address indicated in your medical records and reach out to you directly.

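### The covariate entry rule for the adjusted Aim 1 model has its inequality reversed and names no candidates; the consequence is minor

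*Combined protocol and SAP*

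**What the plan says.** All references are to the combined protocol and SAP.

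- **Unadjusted comparison** (Data and Statistical Methods, Aim 1): "Rates of postoperative urinary retention will be compared between groups using chi squared testing".
- **Adjusted model** (same paragraph): "To adjust for other factors that may impact voiding trial results, logistic regression analysis will be performed". This model "will include variables identified as significant (p>0.01) on univariable analysis as well as intraoperative narcotic use, age, and estimated blood loss". Three covariates are therefore fixed by name, and the rest are chosen by a univariable p-value.
- **Possible sources of candidates** (Study Entry and Recruitment): "Demographic information including age, weight, height, body mass index (BMI), allergies, obstetrical, gynecological, medical, and surgical history will be collected", and "Preoperative bladder testing obtained as part of routine clinical care will also be recorded". Table 1 also has open rows for demographic and intraoperative factors. None of these is designated for screening.
- **Aim 2** has its own named covariates and a different rule: "Anything found to be different at baseline will also be included as covariates". It gives no p-value, so it cannot supply the one for Aim 1.
- **Timing of allocation** (Study Entry and Recruitment): "Patients will be randomized in the preoperative area on the day of surgery".

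**The concern.** A variable is ordinarily called significant when its p-value falls below a threshold, but the rule prints the opposite sign. An analyst who followed it to the letter would fill the model with noise and leave out the factors that best predict failure. This is the only planned adjusted model of the primary outcome, so its content should be readable from the plan.

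Reversing the sign cures the contradiction but leaves two smaller gaps. The value 0.01 appears once, next to a symbol that is already wrong, and nothing else in the documents confirms it. The set of variables to be screened is not stated. At stake are the reproducibility of the adjusted odds ratio and, on the literal reading only, its stability.

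**Working it through.** **1. The plan's own figure.** Sample Size Calculation gives 35% retention, a 20% reduction, two-sided alpha 0.05, 80% power, 72 per group, and 75 per arm after 5% loss. Taking the reduction as 20 percentage points (35% to 15%):

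n = [1.960·√(2·0.25·0.75) + 0.842·√(0.35·0.65 + 0.15·0.85)]² / 0.20² = (1.200 + 0.501)² / 0.04 ≈ 72.4.

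This agrees with 72 (73 if rounded up). The entry rule plays no part in this calculation.

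**2. Expected failures.** 75·0.35 + 75·0.15 = 26.25 + 11.25 = 37.5. Treatment arm plus the three named covariates makes 4 terms, or 37.5/4 ≈ 9.4 failures per term. The quoted sentence does not list treatment arm; I take it to be in the model because the stated purpose is adjustment.

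**3. Number of candidates.** Not in the documents. I assume 5 to 20, with 9 as an anchor: the eight listed headings other than age (weight, height, BMI, allergies and four histories), plus bladder testing.

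**4. Expected size of the model.** An unrelated variable has a roughly uniform p-value, so with k candidates:

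- literal p>0.01: 4 + 0.99k terms, which is 8.95, 12.91 and 23.80 for k = 5, 9 and 20;
- p<0.01: 4 + 0.01k terms, which is 4.05, 4.09 and 4.20.

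**5. Effect on the treatment estimate.** Simulation of 4,000 trials per setting, 75 per arm, failure rates 35% and 15%, with k independent normal candidates unrelated to outcome and every rule applied to the same trials:

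| | k = 5 | k = 9 | k = 20 |
|---|---|---|---|
| No screen: mean log-OR | 1.172 | 1.179 | 1.167 |
| p<0.01: terms | 4.04 | 4.06 | 4.16 |
| p<0.01: paired change in log-OR | 0.000 | 0.001 | 0.002 |
| Literal p>0.01: terms | 8.96 | 12.94 | 23.84 |
| Literal: failures per term (37.5/terms) | 4.2 | 2.9 | 1.6 |
| Literal: mean log-OR | 1.222 | 1.273 | 1.421 |
| Literal: paired change in log-OR | 0.050 | 0.094 | 0.255 |

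The between-trial SD of the log-OR without a screen is about 0.44, so the p<0.01 change is far below anything detectable in one trial.

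**6. Loss of real predictors under the literal rule.** For a normal predictor with odds ratio 2.0 per SD (n = 150, 25% overall failure), the univariable p falls below 0.01 in 79.6% of simulated trials. The literal rule would therefore keep it in only 100 − 79.6 = 20.4%.

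**The case against.** The best defence is that this is a one-character slip. The word makes the intent plain, the number 0.01 is printed, and the natural correction is p<0.01. On that correction the model is almost the same as arm plus the three named covariates, and the treatment estimate does not move in any practical sense. The main comparison is the chi-squared test, and three covariates are already fixed. An error in reading the symbol from the PDF cannot be fully excluded, although nothing in the text suggests one. All of this stands, and it sets the severity.

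A reader might go further and infer that the plan gives no cut-off, so that p<0.01, p<0.05 and p<0.10 are all open. Under that premise, p<0.01 and p<0.10 select different covariate sets in 37% to 85% of simulated trials, and they disagree on significance in 2.0% to 5.0% at the planned effect. Reporting the most favourable of the three cut-offs adds 0.3 to 1.0 points of type I error. The documents do not support the premise: 0.01 is printed, and neither 0.05 nor 0.10 is mentioned for covariate entry. The 0.05 in Sample Size Calculation is the design alpha. The type I increase also requires an analyst to fit all three models and choose among them; any single cut-off left type I error within about 0.1 points of no screen.

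The defence does not remove two facts. The rule is wrong as printed, and the candidates are unnamed. It is also fair to say that the place of narcotic use and blood loss in the model is separate from the sign error. I raise it under the fix because the same sentence would be rewritten.

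**Conclusion.** The stated rule is faulty and should be corrected, but the severity is minor. On the very probable intended reading, p<0.01, the log-OR changes by about 0.000 to 0.002. The literal reading would give about 9 to 24 terms on about 37 failures and raise the log-OR by about 0.05 to 0.26. Those figures show why the sentence cannot stand; they do not forecast what the sponsor will do.

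It might also be inferred that the primary result is at risk. It is not: the chi-squared comparison and the sample size do not use this model.

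The numbers rest on the planning rates, on an assumed 5 to 20 candidates, and on candidates simulated as independent and unrelated to outcome. Weight, height and BMI are in fact related, and each history is more than one variable, so the simulated values are illustrative. The contradiction between word and sign, and the absence of a candidate list, rest on the text alone.

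**What to change.** **Minimum.** In the Aim 1 paragraph, correct the inequality to p<, confirm the cut-off, and list the variables to be screened. Do this before unblinding, and preferably before the interim comparison of failed voiding trials by arm described in the Data and Safety Monitoring Plan.

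**Preferred.** Drop the univariable screen. Pre-specify a logistic model with treatment arm and a short list of covariates known before randomisation and already recorded, for example:

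- age;
- planned anterior repair, since eligible patients are those "scheduled to undergo a retropubic midurethral sling with or without concomitant anterior repair";
- preoperative post-void residual, whose range is limited to below 150 mL by the exclusion criterion.

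Intraoperative narcotic use and estimated blood loss arise after randomisation, so allocation could influence them. Report the model that contains them as a sensitivity analysis.

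**Cost.** Wording only, with no new data, patients or procedures. The one downside is that other candidate predictors of voiding failure move to an exploratory table.

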Our current practice of midurethral sling placement involves injection of lidocaine with epinephrine into the retropubic and suburethral space with the threefold purpose of hydrodissection, hemostasis, and pain reduction. Interestingly, several studies report varying rates of postoperative urinary retention and postoperative pain depending on the type of local anesthetic used (if any) for hydrodissection: however. the data is sparse and invites a more thorough investigation. For example, one study investigated the use of bupivacaine versus normal saline injected suburethrally on postoperative voiding function and pain in patients undergoing retropubic midurethral sling. These authors found no difference in voiding dysfunction between the study and placebo groups; however, the use of bupivacaine did lower pain scores at 6 hours postoperatively. A similar study compared urinary retention and pain control when bupivacaine versus saline for hydrodissection is used while placing tension-free vaginal tape midurethral slings. Hydrodissection fluid was placed subcutaneously, into the space of Retzius bilaterally, suburethrally, and periurethrally. These authors concluded that bupivacaine did not increase the risk of failing a postoperative voiding trial; however, there was a trend toward a difference with a 19% reduction in voiding trial success (47% pass rate in the bupivacaine group vs 66% in the saline only cohort, p = 0.14) and a statistically significant elevated PVR in the bupivacaine group compared with the control group. In addition, bupivacaine was not seen to improve immediate postoperative pain after placement of a tension-free vaginal tape. A third study reported that while bupivacaine did decrease postoperative pain scores following retropubic midurethral sling placement, reported pain was in fact low in both the intervention and placebo groups. Of note, there was also a trend toward increased voiding trial failure in the bupivacaine group (33% vs 18% in the controls (p = 0.082)). In this study, injections were performed into each of the two trocar paths "deep behind the pubic bone" and into the vaginal incision.

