The aforementioned studies vary considerably in the quantity and composition of local anesthetic used intraoperatively, the location of injection, and in the administration of voiding trials postoperatively. Sample size of each study was also small and thus perhaps underpowered to detect statistically significant differences. Therefore, based on the limited existing data, we hypothesize that patients receiving retropubic normal saline compared to local anesthetic (e.g., lidocaine) will have a reduction in rates and duration of postoperative urinary retention following retropubic midurethral sling placement.

**Aim 1**: to compare the incidence of urinary retention following retropubic midurethral sling placement in those women receiving normal saline vs lidocaine for retropubic hydrodissection. We will compare rates of failed retrograde voiding trials between patients receiving normal saline and those receiving the same quantity of lidocaine. This will be completed using a standardized retrograde voiding trial 1-2 hours postoperatively (as outlined in "Data and Statistical Methods" below). We hypothesize that patients receiving normal saline will have a reduction in postoperative urinary retention following retropubic midurethral sling placement.

**Aim 2**: to assess postoperative pain in women receiving retropubic normal saline vs lidocaine during midurethral sling placement. Postoperatively, subjects will be asked to assess their pain using a VAS scale administered by nursing personnel at 2 hours (+/- 30 minutes) and again at 6 (+/- 30 minutes) hours following surgery, during the time of routine vital sign assessment. The subsequent pain assessments will be completed by the patient via an at-home form from discharge through postoperative day #7. Narcotic use will be queried through the electronic medical record as well as with a pain diary administered at time of discharge until postoperative day #7.

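### The Aim 1 regression adjusts for intraoperative narcotics and blood loss, which arise after randomization, so an arm odds ratio read from it need not be the total treatment effect (low priority)

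*Combined protocol and SAP*

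**What the plan says.** Under Data and Statistical Methods, Aim 1 compares retention rates between arms by chi-squared test. It then adds: "To adjust for other factors that may impact voiding trial results, logistic regression analysis will be performed". That model takes variables that pass a univariable screen "as well as intraoperative narcotic use, age, and estimated blood loss".

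For Aim 2, arms are compared on change in VAS and on narcotic requirements by t-test (rank-sum for narcotics if needed). A separate model is described thus: "Multivariable logistic regression analyses will be used to identify independent risk factors that predict pain at 2, 6 and 24 hours postoperatively". Its covariates follow: "We plan to adjust for operating time, estimated blood loss, urinary retention, and concomitant procedures", with the reason given as "as all of these may predict worse postoperative pain".

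Other sections bear on this:
- **Study Entry and Recruitment:** patients are randomized preoperatively on the day of surgery. The assigned syringe is injected during the operation. Surgical and anesthesia teams are blinded. Suburethral anesthetic is optional.
- **Narcotic requirements and Table 1:** doses given during surgery count towards the narcotic measure.
- **Background/Hypothesis:** current practice injects lidocaine with epinephrine for a "threefold purpose of hydrodissection, hemostasis, and pain reduction". The Aim 1 hypothesis is: "We hypothesize that patients receiving normal saline will have a reduction in postoperative urinary retention following retropubic midurethral sling placement".
- **Potential Risks, Issues, and Solutions:** no difference in bleeding is expected, because both syringes contain epinephrine.

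**The concern.** Randomization balances what exists before the injection. A variable measured later may itself respond to the injection. Holding it fixed has two consequences:

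- Any part of the arm effect that acts through the variable is removed from the arm coefficient.
- If an unmeasured factor drives both the variable and the outcome, patients matched on the variable are no longer comparable between arms. An arm effect can then appear where none exists.

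For Aim 1 the variable at issue is intraoperative narcotic use. The plan treats it as part of an outcome in Aim 2 and as a covariate in Aim 1. At stake is the reading of an adjusted odds ratio printed beside the chi-squared result. A reader could see that the two differ but not why, and the plan does not say which governs.

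**Working it through.** **1. Timing of the covariates**

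| Variable | Model | Fixed before injection? | Arm effect in the documents |
|---|---|---|---|
| Age | Aim 1 | Yes | Not possible |
| Intraoperative narcotics | Aim 1 | No; nothing limits it to doses given before the injection | Plausible from the pain-reduction purpose; not stated |
| Estimated blood loss | Aims 1 and 2 | No | None expected |
| Operating time | Aim 2 | No | No path given |
| Urinary retention | Aim 2 | No | Hypothesised (Aim 1) |
| Concomitant procedures | Aim 2 | Yes, if planned | Not possible for planned ones |

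**2. The plan's own figure.** The Sample Size Calculation reads: "To detect a clinically significant reduction of postoperative urinary retention of 20" percent, from 35%. Taken as 35% versus 15%, with pooled variance, 80% power and two-sided 0.05:

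n = [1.960·√(2·0.25·0.75) + 0.842·√(0.35·0.65 + 0.15·0.85)]² / 0.20² = (1.200 + 0.501)² / 0.04 ≈ 72.4

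That is 73 rounded up, against 72 stated. A relative 20% reduction (35% to 28%) would need 691, so the reading in percentage points is the one used. The calculation contains no covariates, so this concern does not touch it.

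**3. Aim 1, no true arm effect (assumed inputs).** Retention is 35% in both arms, with 75 per arm. Narcotic use has SD 1 and is shifted by d SD in the saline arm. An unmeasured factor U has correlation 0.5 with narcotic use and doubles the odds of retention per SD. Neither arm nor narcotics affects retention.

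At a given narcotic level, mean U is lower by 0.5·d in the saline arm. The adjusted odds ratio (saline versus lidocaine) is therefore roughly exp(−0.5·d·ln 2). Simulation gives large-sample odds ratios from n = 2,000,000 and rejection rates from 10,000 trials (Monte Carlo SE √(0.05·0.95/10,000) ≈ 0.2 points):

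| d | Formula | Simulated OR | Rejection at 0.05 |
|---|---|---|---|
| 0 | 1.00 | 1.00 | 5.0% |
| 0.1 | 0.97 | 0.97 | 5.7% |
| 0.3 | 0.90 | 0.91 | 5.6% |
| 0.5 | 0.84 | 0.85 | 7.0% |
| −0.5 | 1.19 | 1.18 | 7.0% |

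Across all the Aim 1 scenarios run, the chi-squared test rejected in 4.6% to 5.7%. Shifts up to 0.3 SD are therefore hardly distinguishable from nominal.

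**4. Aim 1, narcotics on the causal path (assumed inputs).** Here narcotics raise retention, and a direct arm effect is built to cancel that exactly, so the total effect is null. With d = 0.3 and 1.5-fold odds per SD, the adjusted OR is 0.88 and rejection 6.2%. With d = 0.5 and 2-fold odds, deliberately extreme, they are 0.71 and 14.5%. These are correct direct effects; they mislead only if read as total effects.

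**5. Aim 2, if an arm effect were read from it (assumed inputs).** The plan gives no pain cut-point, so pain prevalence is assumed. Retention is 35% versus 15%, pain is 30% without retention, retention doubles the odds of pain, and arm acts only through retention.

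- Pain if retained: odds 2·(0.30/0.70) = 0.857, so 46.2%.
- Lidocaine: 0.65·0.30 + 0.35·0.462 = 0.357.
- Saline: 0.85·0.30 + 0.15·0.462 = 0.324.
- Total OR: (0.324/0.676)/(0.357/0.643) ≈ 0.87. The retention-adjusted OR is 1.00.

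With 1.5-fold or 3-fold odds the total OR is 0.92 or 0.80. On a linear VAS scale, a 10 mm effect of retention would remove 10·(0.35 − 0.15) = 2 mm from the arm difference.

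**6. Order of events at 2 hours.** Table 1 puts the voiding trial and the VAS in the same 2 h ± 30 min column. A VAS at 1.5 h could precede a voiding trial at 2 h, so retention need not come before the pain score it is meant to explain.

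**The case against.** The between-arm conclusions rest on the chi-squared test and the t-tests, all unadjusted. Harm requires arm to be in a regression and its coefficient to be read as a total effect, and the plan states neither. The Aim 2 model is introduced as a search for risk factors, which largely answers that half. For Aim 1 the path is thin:

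- Anesthesia teams are blinded, so knowledge of allocation cannot drive dosing.
- Doses given before the injection cannot respond to it.
- Optional suburethral anesthetic may shrink any difference.
- The Background reports mixed evidence that local anesthetic reduces pain here.

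Most of this stands, and it sets the priority. It does not remove the Aim 1 point. Blinding does not stop a physiological response to less anesthesia from changing narcotic use. Adjusting for other factors, stated straight after the between-arm test, most naturally means other than arm; that is an inference. Intention to treat settles who is analysed, not which covariates are admissible.

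A reader might infer that the Aim 2 model conditions on a causal path the plan asserts. The plan says only that retention may predict pain, which is not a causal statement. A reader might also add the one-hour voiding allowance to the 1-2 hour timing and place the end of the voiding trial at 3 hours. The text says the trial is completed at 1-2 hours, so only the shared Table 1 window is secure.

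**Conclusion.** The point holds for Aim 1 in conditional form. The model forces in two post-randomization variables, one of which arm could plausibly affect, and an arm odds ratio from it need not be the total treatment effect. For Aim 2 it is a secondary caution, relevant only if an arm effect is taken from the risk-factor model.

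The documents give neither the size nor the direction of any distortion. Every narcotic shift, correlation and odds ratio above is assumed. Under the shared-cause null, inflation is negligible up to a 0.3 SD shift and about 2 points at 0.5 SD.

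It would be tempting to conclude that the primary result is biased or the trial underpowered. The documents do not support that: the chi-squared test, the t-tests and the sample size use none of these covariates. Nor do they support a claim that blood loss differs by arm. This is a cheap improvement of low priority.

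**What to change.** Amend Data and Statistical Methods in three places:

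1. State that the unadjusted chi-squared comparison governs the Aim 1 conclusion.
2. Limit any model used to estimate an arm effect to prespecified variables fixed before the injection and already collected, such as age and planned anterior repair, plus baseline VAS for pain. Apply the same limit to variables entering through the univariable screen, if it is kept.
3. Keep models containing intraoperative narcotics, blood loss, operating time or urinary retention as exploratory risk-factor models, and state that no arm effect is claimed from them.

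The cost is wording only: no new data, no change in sample size and no planned between-arm test lost. The one downside is that the intraoperative variables move to an exploratory analysis.
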